A Clinical Trial of Silver Diamine Fluoride to Arrest Early Childhood Caries in Young Children

NCT04054635

Study Protocol and Statistical Analysis Plan

15 April 2019

Purpose:

To investigate the effectiveness of using silver diamine fluoride (SDF) to arrest early childhood caries in very young children randomized to different application frequency regimens. We will also study potential oral microbiome changes in children receiving SDF treatment.

Hypotheses:

1. Two applications of SDF at different frequencies will yield similar arrest rates.
2. SDF will negatively influence the population of cariogenic bacteria in the oral microbiome.

Objectives (*primary objective, †secondary objectives):

1. Determine the effectiveness of various application regimens of SDF to arrest caries*;
2. Determine potential changes to the oral microbiome in young children†; and
3. Determine the impact on early childhood oral health related quality of life†.

Methods:

Design: We propose a RCT to study the use of SDF to arrest cavitated caries lesions in primary teeth at different application regimens. Regimen 1 will be two applications of SDF four months apart, which is the protocol frequency adopted by the Winnipeg Regional Health Authority's Clinical Guideline on SDF. This frequency was used in a pilot study. Regimen 2 will be two applications of SDF six months apart (American Dental Association's [ADA] recommendation). Regimen 3 will be two applications of SDF one month apart, which is proposed in the American Academy of Pediatric Dentistry's clinical practice guideline. The ADA recently indicated that SDF should be prioritized over 5% NaFV for nonrestorative management of cavitated lesions. Thus, we will not include a control group to receive fluoride varnish as this would now be considered unethical and substandard care. However, we will attempt to follow as a comparison group those children whose parents/caregivers do not consent to SDF to manage their child's caries and only choose 5% NaFV.

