Arrest of caries lesions will be determined by assessing clinical hardness, colour change, and size of lesions at baseline, at second visit, and at the final study visit. Children will be recruited and we will perform block randomization by site in order to achieve equal proportions in each regimen by clinic site of recruitment. Study visits will occur at the Children's Hospital Research Institute of Manitoba (CHRIM) or at community-based dental clinics. Following informed consent the child's parent/caregiver will complete a short questionnaire (via interview) on general and dental health, oral hygiene, dietary intake of sugars, and family demographics along with the ECOHIS to assess OHRQL. SDF will be applied on the day of recruitment to cavitated lesions involving dentin followed by 5% NaFV. Depending on which frequency regimen children are randomized to, they will return for a second visit. During this second visit, caries lesions treated with SDF at baseline will be assessed to see if caries is arrested as determined through measures of hardness, colour change, and size. At this same visit a second application of SDF will be applied to these initially treated caries lesions followed by 5% NaFV. Children and parents will return for the third and final study visit according to the schedule of their randomized grouping. Parents/caregivers will complete a follow-up questionnaire similar to the

baseline tool. Caries lesions previously treated by SDF will be assessed for clinical hardness, colour change and size to determine if they have arrested.

Population: As ECC is age specific, participants will be < 72 months of age with active caries and their parents/caregivers. The majority will be recruited from community-based dental clinics in Winnipeg (i.e., Access Downtown, Mount Carmel Clinic, and SMILE Plus Children's Dental Clinic) or who are currently on a wait list for dental surgery under general anesthesia in Winnipeg. We found that these were ideal sites for our recently completed feasibility trial of SDF. We will restrict participation to children living in the Winnipeg region or within a one hour drive of Winnipeg to minimize the risk of loss-to-follow-up. Eligibility criteria are designed to select young children who have active caries, and thus are at an increased risk of morbidity from existing caries and onset of new caries.

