The Early Childhood Oral Health Impact Scale (ECOHIS) will be used to assess changes in OHRQL from baseline to completion of study. ECOHIS is a validated tool for use with parents/caregivers of children < 72 months of age. It consists of 13 questions grouped into two sections: 1) child impact, and 2) family impact. The child impact section includes nine questions in four areas: 1) symptoms, 2) functions, 3) psychology, and 4) self-image and social interaction. The family impact component covers two areas: 1) parental distress and 2) family function. Each question is scored from 0 to 5 [0= never, 1= hardly ever, 2= occasionally, 3 = often, 4= very often, 5= don't know]. A total score for each child is calculated by summing up response codes. The ECOHIS will allow us to calculate and compare mean ECOHIS scores at each visit and between groups. Our team has experience with analyzing ECOHIS.

Clinical outcomes assessed will include the proportion of teeth arrested (i.e., "arrest rate" = total number teeth arrested / total number of teeth treated), the proportion of children with any arrested caries, associated morbidity (dental pain and, dental abscess assessed using the PUFA index), and proportion of children requiring dental surgery under GA. The PUFA index is a score of the consequences of severely decayed teeth with visible pulpal involvement (P/p), ulceration caused by dislocated tooth fragments (U/u), fistula (F/f) and abscess (A/a). We will also record dmft and dmfs scores for each child at baseline and at subsequent study visits. The dmft and dmfs scores are cumulative counts of the total number of primary teeth or surfaces decayed, missing due to, or filled because of caries.

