Our research staff will contact interested parents/caregivers and will inform them of the study objectives, eligibility criteria, and procedures. Children will undergo a dental screening by the principle investigator or a calibrated and trained dental examiner to determine whether children meet the clinical criteria for this study by having cavitated caries lesions involving dentin (i.e. ICDAS category 5 or 6). Since ECC is more common in disadvantaged populations, we will arrange for transportation (i.e., taxis) for participants. We also anticipate that some participants will be newcomers and will require interpreters. We will arrange for WRHA interpreters when needed. Visits will occur at the principle investigator's dental suite at CHRIM or at one of the community-based clinics.

Baseline visit: Following written informed consent, children will be randomly allocated into one of three groups using sealed envelopes to ensure random allocation. Parents/caregivers will complete the baseline questionnaire administered by interviewer. Children will undergo a dental examination (without x-rays) to record the number of teeth and tooth surfaces with caries meeting ICDAS 5 or 6 criteria and the specific tooth numbers. We will record the location, size, hardness, colour, and activity status of each eligible caries lesion. We will also assess the total number of primary teeth and tooth surfaces affected by caries (i.e., dmft and dmfs). We will also determine the PUFA index. SDF will then be applied with a microbrush for one minute to each cavitated lesion meeting the eligibility criteria followed by 5% NaFV.

Second visit: Depending on the regimen children will return 4 months (Regimen 1), 6 months (Regimen 2), or 1 month (Regimen 3) later for their first follow-up visit and second application of SDF. Parents/caregivers will complete the ECOHIS tool. Prior to the second application of SDF, caries lesions that received the first application of SDF will be assessed to determine if caries is arresting. Lesions will be assessed for colour change, size, and hardness. Clinical data will be recorded including dmft, dmfs, and PUFA scores will be recorded. Following the dental assessment of the lesions under investigation, SDF will be applied to these lesions for one minute followed by 5% NaFV.

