PowerSoil Kit (Qiagen). It allows the isolation of genomic DNA (gDNA) from fungi and Gram (+-) bacteria, which will be used for downstream analyses. For the 16S rRNA (bacteriome) and ITS1 rRNA (mycobiome) amplicon sequencing, isolated gDNA will be used for PCR amplification of the V4 region of the bacterial 16S rRNA gene, and for PCR amplification of the fungal Internal Transcribe Spacer 1 (ITS1) rRNA gene. gDNA will be sequenced at Génome Québec using paired-end Illumina MiSeq PE250 sequencing. Data analysis will be performed in the [name] lab using established methods. Briefly, demultiplexed raw sequencing results will be filtered and clustered into operational taxonomic units (OTUs) and alpha and beta diversity analyses performed using QIIME2 (Quantitative Insights into Microbial Ecology) v. 2018.11. 16S sequences will be aligned and taxonomy assigned with the HOMD database. ITS1 sequences will be aligned and taxonomy assigned with the UNITE database.

Data Analysis:

This study will estimate the success of different SDF. Descriptive statistics will be used (e.g. frequencies, proportions, and means \pm standard Deviations). The “arrest rate” (primary outcome) will be calculated for the second visit and again at the third and final visit. Bivariate analyses will assess changes in clinical measures and survey data from baseline to the follow-up. McNemar’s test will be used to compare the arrest rate between the second and third clinical visits and to compare dichotomous data from the baseline questionnaire with that from the follow-up questionnaire within each regimen. Chi-squared analysis will compare arrest rates between the regimen groups. Paired t-test will be used to compare normally distributed interval data from the baseline questionnaire with that from the follow-up questionnaire within regimens (Mann-Whitney test if not normally distributed). We will rely on repeated measures analysis of variance to assess changes in ECOHIS scores and other continuous data over time (i.e. baseline vs. second visit vs. final study visit) within each regimen group and to assess differences between regimen groups. Although this is a pilot RCT, we will explore potential changes in the oral microbiome of those randomized to different regimens. This will provide insights into potential mechanisms of SDF action, whether it has antimicrobial activity and influences the oral microbiome composition. A p value ≤ 0.05 will be significant.

Ethics:

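### The between-regimen ECOHIS analysis treats the pre-treatment score as a response level and names no regimen test; adjusting for baseline would be more efficient at almost no cost

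*Combined protocol and SAP*

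**What the plan says.** Quality of life is a secondary objective: "Determine the impact on early childhood oral health related quality of life". Under Instrumentation and Outcome Measures, ECOHIS "will be used to assess changes in OHRQL from baseline to completion of study", and the team intends to "calculate and compare mean ECOHIS scores at each visit and between groups".

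The score is collected before treatment: under Methods (Design), the parent completes a questionnaire after consent "along with the ECOHIS to assess OHRQL", and SDF is applied on the same day. At the second visit, "Parents/caregivers will complete the ECOHIS tool", before the second application. The final-visit score follows from the Instrumentation text and from the visits listed in Data Analysis.

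Data Analysis states: "We will rely on repeated measures analysis of variance to assess changes in ECOHIS scores and other continuous data over time", and defines the time factor and the use of the model as "i.e. baseline vs. second visit vs. final study visit) within each regimen group and to assess differences between regimen groups". Baseline is therefore one of three response levels in the model that also compares regimens. No baseline covariate and no equal-baseline constraint appears anywhere, and the term that serves as the regimen test is not named.

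**The concern.** Baseline ECOHIS precedes any SDF, and allocation is random, so the expected regimen difference at that visit is zero. A response level that cannot carry a treatment effect adds nothing to the regimen comparison as an outcome, but it is informative as a predictor of the later scores.

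The model offers two between-regimen tests, and each has a cost. The main effect averages the null visit with the two follow-ups. The interaction uses contrasts of the change type, which are noisier than contrasts conditional on baseline, and spreads them over 4 df.

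What is at stake is the chance of detecting a regimen difference in quality of life, and the width of its confidence interval, in a trial with about 22 evaluable children per regimen whose size was set on arrest rates. Leaving the term open also lets the choice between two tests with quite different power be made after the data are seen. The same applies to the other continuous measures put through this ANOVA.

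**Working it through.** **The plan's own figures.** Allowing for 20% loss, 22/0.80 = 27.5, rounded up to 28 per group, as stated. Likewise 22 × 3 × 6 = 396 lesions, as stated. No SD, effect size, correlation or power is given for ECOHIS, so there is no ECOHIS figure to reproduce.

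**Inputs.** From the documents: n = 22 evaluable children per regimen (66 in all), three regimens, three visits, significance level 0.05. Assumed: unit SD, equal correlation r between visits, all visits complete, one regimen differing from the other two by d, and no expected difference at baseline. The visit description lists allocation before the baseline questionnaire, so the last assumption also takes it that knowing the return schedule does not alter parents' answers.

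**Size of the estimate.** Averaging visit differences (0, d, d) gives a main effect of 2d/3.

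**Variance for estimating d, effect at both follow-ups (units of σ²):**

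| | formula | r = 0.3 | r = 0.5 | r = 0.7 |
|---|---|---|---|---|
| Main effect, rescaled to d | 3(1+2r)/4 | 1.20 | 1.50 | 1.80 |
| Follow-up mean minus baseline | 3(1−r)/2 | 1.05 | 0.75 | 0.45 |
| Follow-up mean adjusted for baseline | (1+r)/2 − r² | 0.56 | 0.50 | 0.36 |

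Relative to the adjusted follow-up mean, the main effect needs 2.1, 3.0 and 5.0 times the sample, and the change contrast 1.9, 1.5 and 1.25 times. For the final visit alone at r = 0.5, the change-score variance is 2(1−r) = 1.0 and the adjusted variance is 1 − r² = 0.75.

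**Power (noncentral F).** The squared regimen effects about their mean sum to b = 2d²/3. With the difference at both follow-ups:

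- main effect: λ = n·b·(2/3)² / [(1+2r)/3], on 2 and 63 df
- interaction: λ = n·b·(2/3) / (1−r), on 4 and 126 df
- adjusted final visit: λ = n·b / (1−r²), on 2 and 62 df
- adjusted follow-up mean: λ = n·b / [(1+r)/2 − r²], on 2 and 62 df

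Worked case, d = 0.75 and r = 0.5: b = 0.375 and n·b = 8.25, so λ = 5.5, 11.0, 11.0 and 16.5, and power is 52%, 74%, 83% and 95%. The interaction and the adjusted final visit share the same λ here; the gap between them is the price of 4 df instead of 2.

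If the difference appears only at the final visit, (2/3)² becomes (1/3)² for the main effect, the adjusted follow-up mean takes a factor (1/2)², and the other two λ are unchanged.

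| r from 0.4 to 0.7 | main effect | interaction | adjusted final visit | adjusted follow-up mean |
|---|---|---|---|---|
| d = 0.75, both follow-ups | 57-45% | 65-94% | 79-95% | 94-99% |
| d = 0.50, both follow-ups | 28-22% | 31-60% | 43-65% | 62-80% |
| d = 0.75, final visit only | 17-14% | 65-94% | 79-95% | 38-54% |

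**Simulation check.** With 8,000 trials per setting, d = 0.8 at both follow-ups and r = 0.3 / 0.5 / 0.7, simulated power was 0.68 / 0.58 / 0.51 for the main effect, 0.64 / 0.81 / 0.97 for the interaction and 0.95 / 0.97 / 0.995 for the adjusted follow-up mean. With no effect, all three rejected in about 5% of trials.

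**The case against.** The strongest reply is that the interaction is a natural reading of an analysis described as assessing change over time, and that it already does most of the work. Against it, the adjusted final-visit contrast at 0.75 SD gains about 13 points at r = 0.4, 9 at r = 0.5 and 1 at r = 0.7. That stands. A reader might infer that any regimen difference is diluted; this is true only of the main effect, and the plan does not say that the main effect is the test.

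A reader might also infer that a chance baseline imbalance carries over in full. In the main effect it enters with weight one third, and type I error stays near 5% for every test considered.

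The assumed effect is generous, since every regimen gives two applications of the same agent. At 0.5 SD the adjusted final-visit contrast reaches only 43-65%. Adjustment improves the comparison but does not make the trial well powered for ECOHIS.

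Nor is the whole quality-of-life objective at risk. Change from baseline to completion within a regimen needs baseline as a response level, and that part of the plan is sound. ECOHIS is secondary, and the plan calls the study a pilot RCT.

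Finally, adjustment does not remove a separate difficulty. With equal intervals before and after the second application, the final visit falls at about 1 + 1 = 2, 4 + 4 = 8 or 6 + 6 = 12 months after baseline. Any final-visit contrast therefore also reflects elapsed time, most plainly for the cumulative dmft and dmfs.

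None of this supports leaving the regimen test unnamed or leaving out a baseline score that is already collected.

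**Conclusion.** The point holds as one of efficiency and specification, for the between-regimen comparison only. The plan leaves the regimen test open between a main effect that shrinks the difference to two thirds and an interaction that spends 4 df on change-type contrasts. The baseline-adjusted final-visit contrast has more power than both at every correlation checked from 0.3 to 0.7, by a wide margin over the main effect and a narrow one over the interaction when correlation is high.

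The 94-99% figure should not be read as the general gain from adjustment. It belongs to the adjusted mean of both follow-ups when the difference is present at both; if the difference appears only at the final visit, that contrast drops to 38-54%, below the interaction. The choice of contrast therefore matters as much as the covariate.

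All power figures rest on assumed effect sizes, equal correlation between visits and complete data. The documents do not support a claim of bias or of a false-positive problem.

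**What to change.** In Data Analysis, replace the between-regimen part of the ECOHIS analysis along these lines: ECOHIS at the second and final visits is the response; baseline ECOHIS is a covariate; regimen, visit and regimen-by-visit are factors; child is the repeated unit. A model that keeps baseline as a response but constrains its means to be equal across regimens is an acceptable alternative of about the same efficiency.

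Pre-specify one between-regimen contrast (the adjusted final visit, or the adjusted mean of both follow-ups), give the reason for the choice, and report it with a 95% CI.

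Treat dmft and dmfs in the same way. Lesion size is recorded per lesion, at about six per child, so its model also needs a lesion-within-child level.

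Keep the within-regimen analysis of change over time as planned. State in the analysis plan and in the report that visits fall at different times after baseline by regimen (final visit at about 2, 8 or 12 months), so the contrast reflects elapsed time as well as regimen.

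For ECOHIS the cost is wording and one error degree of freedom (63 to 62); no further data or children are needed.

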Sample and Justification of Sample Size: Sample size for this pilot study has been determined in discussion with [name] (collaborator, Professor & Biostatistician). Our intent is to compare arrest rates between groups and to see whether the three different regimens will yield arrest rates within a range of what we will determine to be clinically acceptable. Based on our recent pilot feasibility study of SDF with 40 children (with 239 lesions) we reported an arrest rate of approximately 96% following two applications of SDF. Results from a recent systematic review state that 80% of lesions can arrest because of SDF. We believe that a range of arrest rates from 80% to 96% yield similar beneficial outcomes in the clinical setting. Based on our pilot study, 40 children had 239 lesions (average 6 lesions/child). With our pilot sample of 239 lesions, it is possible to estimate an arrest rate with a 95% confidence interval to be accurate within $\pm 6.5\%$. With 400 lesions anticipated in our proposed recruitment sample, the 95% confidence interval for the arrest rate would be $\pm 5.0\%$. We propose three SDF regimen groups and anticipate that each group will have 22 children anticipating an average of six lesions. This would mean 396 lesions would be followed in this study. We anticipate that with 400 lesions the percent of arrest will be within $\pm 5\%$ if we have 22 children in each group. To deal with potential drop-outs and loss-to-follow-up of up to 20% we will over recruit by into each group and recruit 28 per group. We anticipate that we can successfully recruit 10 children each month.

Instrumentation and Outcome Measures: Baseline and follow-up visit questionnaires will be a modified versions of those used in our SDF pilot feasibility study (developed by [name] [collaborator] in her SDF efficacy study). The questionnaire collects child and family

demographic information, oral hygiene and use of toothpaste, dietary habits (i.e., snack foods and drinks), consumption of fluoridated water, appearance of the teeth, and symptoms (e.g., pain). The tools also include sections for the parent/caregiver to complete with their child on how the child believes their teeth look and feel and how they rated their visit and SDF treatment.

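### Repeated measures ANOVA for ECOHIS in its standard form drops any child missing a visit; a mixed model would keep the observed scores at almost no cost

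*Combined protocol and SAP*

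**What the plan says.** The third objective, marked secondary, is to "Determine the impact on early childhood oral health related quality of life". Under Instrumentation and Outcome Measures the plan adds: "The ECOHIS will allow us to calculate and compare mean ECOHIS scores at each visit and between groups".

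The Data Analysis section names a single longitudinal method: "We will rely on repeated measures analysis of variance to assess changes in ECOHIS scores and other continuous data over time". It gives the scope as "i.e. baseline vs. second visit vs. final study visit) within each regimen group and to assess differences between regimen groups", and the threshold as "A p value ≤ 0.05 will be significant".

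On loss, the sample size section says "We propose three SDF regimen groups and anticipate that each group will have 22 children". It then allows for "potential drop-outs and loss-to-follow-up of up to 20" per cent by planning to "recruit 28 per group".

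No section says what happens to a child with an incomplete set of visits. There is no analysis population, imputation rule, mixed model or sensitivity analysis.

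**The concern.** Classical repeated measures ANOVA treats each child as a complete vector of three scores. A child lacking one score is normally removed from the whole analysis, including the visits attended.

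Two things are at stake. The first is precision: scores already collected are not used, although the plan wants mean ECOHIS at each visit and between groups. The second is selection: an analysis of completers is unbiased in general only if loss is unrelated to the scores. Recruiting 28 instead of 22 per group protects the number of completers, but not who they are.

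Unequal loss between arms is plausible though not documented. The visit descriptions under Implementation put the final visit at about 8, 12 and 2 months for Regimens 1, 2 and 3, so children are exposed to dropout for very different lengths of time.

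**Working it through.** **Inputs from the plan.** 22 evaluable and 28 recruited per group; three groups; loss of up to 20%; three visits.

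**Inputs assumed, because the plan gives none.** Within-child correlation ρ of 0.6 to 0.7 (0.4 to 0.6 in the bias simulations); timing of loss; strength of the link between score and loss. Scores are in SD units, with equal variance at each visit.

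**1. The plan's own figure.** 22 / (1 − 0.20) = 27.5, rounded up to 28. This reproduces.

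**2. Children and scores left out at the upper bound.** Recruited: 3 × 28 = 84. Lost: 0.20 × 84 = 16.8, about 17; or 84 − 66 = 18 if exactly 22 per group remain. Taking 18 lost, completers supply 66 × 3 = 198 scores.

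| When the 18 are lost | Scores observed | Discarded |
|---|---|---|
| All before visit 2 | 198 + 18 × 1 = 216 | 18 (8.3%) |
| Half before, half after | 198 + 9 × 1 + 9 × 2 = 225 | 27 (12.0%) |
| All after visit 2 | 198 + 18 × 2 = 234 | 36 (15.4%) |

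**3. Precision within one arm, random loss, n = 28, completers c = 0.8 × 28 = 22.4.** The completers' SE of a change is √[2(1 − ρ)/c]: 0.189 at ρ = 0.6 and 0.164 at ρ = 0.7.

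- *Baseline to visit 2, all losses after visit 2.* All 28 children have both scores, so the SE is √[2(1 − ρ)/28]. The ratio to completers is √(22.4/28) = 0.894, a cut of 10.6% at any ρ.
- *Baseline to visit 2, all losses before visit 2.* The likelihood SE is approximately √[(1 − ρ²)/c + (1 − ρ)²/n]. At ρ = 0.6: √(0.64/22.4 + 0.16/28) = 0.185, a cut of 2.0%. At ρ = 0.7: √(0.51/22.4 + 0.09/28) = 0.161, a cut of 1.5%. The same figures apply to baseline to final under this pattern with equal correlations.
- *Baseline to final, all losses after visit 2, equal correlations.* The residual variance of the final score given the first two is s = 1 − 2ρ²/(1 + ρ), and the SE is approximately √[s/c + (2(1 − ρ) − s)/n]. At ρ = 0.6: s = 0.55, SE = √(0.55/22.4 + 0.25/28) = 0.183, a cut of 3.2%. At ρ = 0.7: s = 0.424, SE = √(0.424/22.4 + 0.176/28) = 0.159, a cut of 3.0%. With correlations varying within 0.6 to 0.7, simulation gave 0.186 against 0.178, a cut of about 4%.

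**4. Precision between two arms.** In simulation (28 per arm, ρ = 0.5, 20% random loss, half of it after visit 2), the SE of the difference in change fell from 0.297 to 0.276 at visit 2 (7%) and from 0.297 to 0.289 at the final visit (3%).

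**5. Bias when loss depends on the last observed score.** Simulated with true change 0, 20% loss, and log-odds of loss 0.7 to 1.1 per SD. Size of the completers' bias in within-arm change:

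| Timing of loss | Change to visit 2, ρ = 0.6 | Change to visit 2, ρ = 0.4 | Change to final |
|---|---|---|---|
| All before visit 2 | 0.05 to 0.07 | 0.08 to 0.11 | about the same as to visit 2 |
| All after visit 2 | 0.05 to 0.08 | 0.08 to 0.11 | about 0 (up to 0.02 if correlations are unequal) |

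The likelihood estimate was within 0.01 SD of the truth throughout.

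**6. Bias between arms (ρ = 0.5, 28 per arm).** With the same loss mechanism and 20% loss in both arms, completer bias cancels (−0.002 SD at the final visit). With 10% against 30% loss it is about 0.05 SD, against 0.01 SD for likelihood; the SE is about 0.30 SD.

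**7. Loss depending on the unseen final score (ρ = 0.5).** Bias in the final change was −0.06 to −0.11 SD for likelihood and −0.01 to −0.08 SD for completers. The mixed model was the worse of the two.

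**The case against.** The strongest reply is that the plan nowhere says only completers will be analysed. That is right. Complete-case use is a property of the named method in its standard form, and the plan is silent on missed visits. A reader might infer that the sponsor has chosen to discard data; the documents do not support that.

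A second reply is that the harm is small. This also stands. A between-arm bias of 0.05 SD is about one sixth of its SE of 0.30, and needs an assumed threefold difference in loss. The 10% gain in precision requires every lost child to have attended visit 2, which nothing in the plan establishes. A reader might infer that the ECOHIS conclusions would be seriously distorted; the figures do not show that.

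Third, 20% is a planning ceiling, and the plan acts to limit loss: residence within an hour of Winnipeg, arranged transport, interpreters, and over-recruitment. These reduce the number lost, but do not decide how those lost are analysed.

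Fourth, a reader might infer that a mixed model cures dropout bias. It does so only when loss depends on observed scores (step 7), so the change of model needs a sensitivity analysis beside it.

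Finally, this is a secondary objective in a study that calls itself a pilot, and the arrest-rate analysis is untouched. That bears on priority, not on whether the better method should be used.

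**Conclusion.** The point holds as a modest one. The named method in standard form would leave out about 17 to 18 of 84 children at the plan's upper bound of loss, although each has at least one score. A likelihood analysis of all observed scores is never materially less precise in these calculations. It cuts the SE by up to about 10% for baseline to second visit and about 2% to 4% for baseline to final. It also removes a within-arm bias of up to about 0.11 SD when loss follows observed scores. It gives no protection when loss follows unseen scores.

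These sizes rest on the assumed correlations, timing and loss mechanism, and on ECOHIS being collected at all three visits as the Data Analysis section implies. Smaller loss than 20% shrinks all of them.

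**What to change.** In the Data Analysis section, replace repeated measures ANOVA for ECOHIS and other continuous outcomes with a linear mixed model:

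- Include every child with at least one score, and all observed scores.
- Fixed effects: visit, regimen, visit-by-regimen, and site, since randomisation is blocked by site.
- Unstructured within-child covariance. Visits are 1, 4 or 6 months apart by regimen, so correlations may differ; let the covariance differ by regimen if it can be fitted, and state the simpler form to fall back on.
- Report loss by regimen and visit.
- Add one simple sensitivity analysis for loss not at random, for example shifting the unobserved scores by a range of fixed amounts in each arm.

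Regimen comparisons at a given visit will still be made at different elapsed times. The mixed model does not change that, and the text should say so.

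The cost is wording, standard software and slightly more analysis work, with no extra children or data. A common unstructured covariance has 6 parameters (3 variances, 3 covariances); one per regimen has 3 × 6 = 18, which is demanding at about 28 per arm and is why a fallback is needed.
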